9.2. Populations for Analyses

The intent-to-treat (ITT) analysis set is defined as all subjects who signed an informed consent form and were enrolled into the study.

The Safety analysis set is defined as all subjects who received any amount of study drug. All safety analyses will be performed using the Safety analysis set.

The Response-Evaluable analysis set is a modified ITT analysis set defined as all subjects with measurable disease at baseline who received study treatment and had at least one post-baseline response assessment or discontinued treatment due to disease progression (including death due to disease progression) within 16 weeks (+ a 2-week window) of the first dose of study treatment. All efficacy analyses will be performed using the Response-Evaluable analysis set.

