- New lesions are considered measurable at the time of initial progression if the longest diameter is at least 10 mm (except for pathological lymph nodes which must have a short axis of at least 15 mm). Any new lesion considered non-measurable at the time of initial progression may become measurable and therefore included in the tumor burden if the longest diameter increases to at least 10 mm (except for pathological lymph nodes which must have a short axis of at least 15 mm). In situations where the relative increase in total tumor burden by 10% is solely due to inclusion of new lesions which become measurable, these new lesions must demonstrate an absolute increase of at least 5 mm.

Subjects should discontinue study therapy upon evidence of confirmed progression. Subjects who discontinue study treatment prior to confirmed progression of disease will continue to undergo radiographic and response assessments per protocol.

Note that all radiographic scans will be collected and archived for potential independent central review of response.

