Response assessment data (ie, progressive disease or no progression of disease) will continue to be collected (based on standard-of-care radiographs) for subjects who have not progressed at the time of the termination visit, until the subject starts alternative anti-cancer treatment or develops progressive disease, whichever occurs first. Response assessment and assessment of tumor markers will be obtained at treatment termination, unless a prior radiographic assessment has been performed within the last 14 days or at a prior response assessment that documented progressive disease. At the investigator's discretion, scans may be performed at any time if progressive disease is suspected.

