9.3.1. Efficacy Analyses

Efficacy analyses will be performed separately for each cohort. RECIST 1.1 criteria will be used for the primary endpoint evaluation ([Eisenhauer et al., 2009](#)), and iRECIST will be used for the exploratory endpoint response evaluation ([Seymour et al., 2017](#)). The iRECIST endpoints are analyzed using the same statistical methodology and the results will be presented in the same ways for the corresponding RECIST 1.1 endpoints.

The primary efficacy endpoint is the ORR defined as the proportion of subjects who achieve confirmed CR or PR per RECIST v1.1. The best overall response is the best response recorded from the start of the treatment until PD. The smallest measurements recorded since the treatment started will be used as the reference for PD. Subjects with CR or PR are considered to have obtained objective response. Subjects with not-evaluable response (NE) are counted as non-responders. Exact 95% CI will be constructed for the ORR for each cohort.

Subjects with CR, PR or SD are considered to have achieved disease control. Disease control rate is defined as the proportion of subjects who have achieved CR, PR, and SD. Duration of response only applies to subjects whose best overall response is CR or PR and is defined as the number of days from the first documentation of objective tumor response to the date of first PD or death due to underlying cancer.

Duration of stable disease is measured from the start of the treatment (the first treatment date for non-randomized studies, the randomization date for randomized studies) until the date when the criteria for overall disease progression are first met.

Duration of response is the time from first evaluation showing CR or PR (response confirmation required at subsequent tumor assessment no earlier than 4 weeks after first evaluation showing CR or PR) to the time of the first subsequent evaluation showing PD or death. Only subjects who experience a confirmed CR or PR will be analyzed for DoR. Subjects who do not experience PD or death will be censored per the censoring rules in the statistical analysis plan.

Progression-free survival is defined as the number of days from Day 1 in Cycle 1 to the first documented progression or death due to any cause. Only deaths that occurred within 30 days of the last progression assessed.

Overall survival is defined as the time from the first dose of study drug to death due to any cause.

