9. STUDY ANALYSIS SETS

The populations defined below will be reviewed against the study database at a DRM at the time of the Final Analysis. The database at this time will be nearly final (i.e., the meeting may result in further data queries/changes post meeting), so inclusion/exclusion of subjects from study populations defined at this meeting will be further checked (post meeting) against a final locked database and will then be finalised prior to reporting.

The following analysis sets are defined:

Population	Description
Safety Analysis Set	All subjects who received any amount of study drug. All safety analyses will be performed using the Safety analysis set.
Intention to Treat (ITT) Analysis Set	All subjects who signed an informed consent form and were enrolled into the study.
Response-Evaluable (RE) Analysis Set	The Response-Evaluable analysis set is a modified ITT analysis set defined as all subjects with measurable disease at baseline who received study drug and had at least one post-baseline response assessment or discontinued treatment due to disease progression (including death due to disease progression) within 16 weeks (+ a 2-week window) of the first dose of study drug. All efficacy analyses will be performed using the Response-Evaluable analysis set

10.PLANNED STATISTICAL METHODS

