13.2. List of Tables

Table Number	Table Title
14.1.1	Participant Disposition – All Subjects
14.1.2.1	Demography – Safety Analysis Set
14.1.2.2	Demography of Cohort F – Safety Analysis Set
14.1.3.1	Baseline Disease Characteristics – Safety Analysis Set
14.1.3.2	Baseline Disease Characteristics of Cohort F – Safety Analysis Set
14.1.4.1	Prior Cancer Treatments – Safety Analysis Set
14.1.4.2	Other Prior Medications – Safety Analysis Set
14.1.4.3	Concomitant Medications – Safety Analysis Set
14.1.5	Investigational Product Exposure – Safety Analysis Set
14.2.1	Response – (RECIST v1.1) – Response Evaluable Analysis Set
14.2.2.1	Duration of Response (RECIST v1.1) – Response Evaluable Analysis Set
14.2.2.2	Duration of Response (RECIST v1.1) – KM – Response Evaluable Analysis Set
14.2.3.1	Duration of Stable Disease (RECIST v1.1) – Response Evaluable Analysis Set
14.2.3.2	Duration of Stable Disease (RECIST v1.1) – KM – Response Evaluable Analysis Set
14.2.4	Response – (iRECIST) – Response Evaluable Analysis Set
14.2.5.1	Duration of Response (iRECIST) – Response Evaluable Analysis Set
14.2.5.2	Duration of Response (iRECIST) – KM – Response Evaluable Analysis Set
14.2.6.1	Duration of Stable Disease (iRECIST) – Response Evaluable Analysis Set
14.2.6.2	Duration of Stable Disease (iRECIST) – KM – Response Evaluable Analysis Set
14.2.7	Progression Free Survival (RECIST) – KM – Response Evaluable Analysis Set
14.2.8	Progression Free Survival (iRECIST) – KM – Response Evaluable Analysis Set
14.2.9	Overall Survival – KM – Response Evaluable Analysis Set
14.3.1.1	Overall Summary of Treatment Emergent Adverse Events – Safety Analysis Set

Table Number	Table Title
14.3.1.2	Treatment Emergent Adverse Events by System Organ Class and Preferred Term – Safety Analysis Set
14.3.1.3	Treatment Emergent Adverse Events by System Organ Class, Preferred Term and Severity – Safety Analysis Set
14.3.1.4.1	Treatment Emergent Adverse Events Related to Etigilimab by System Organ Class and Preferred Term – Safety Analysis Set
14.3.1.4.2	Treatment Emergent Adverse Events Related to Nivolumab by System Organ Class and Preferred Term – Safety Analysis Set
14.3.1.4.3	Treatment Emergent Adverse Events Related to Etigilimab and Nivolumab by System Organ Class and Preferred Term – Safety Analysis Set
14.3.1.4.4	Treatment Emergent Adverse Events Related to Etigilimab or Nivolumab by System Organ Class and Preferred Term – Safety Analysis Set

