13.3. List of Figures

Figure Number	Figure Title
14.1.1	Swimmer Plot of Study Progression – Response-Evaluable Analysis Set
14.1.2	Swimmer Plot of Study Progression – Gynaecological Indications – Response-Evaluable Analysis Set
14.1.3	Swimmer Plot of Study Progression – Rare Tumors – Response-Evaluable Analysis Set
14.2.1.1	Waterfall Plot of Percentage Change from Baseline in the Sum of Diameters – Response-Evaluable Analysis Set
14.2.1.2	Waterfall Plot of Percentage Change from Baseline in the Sum of Diameters – Gynaecological Indications – Response-Evaluable Analysis Set
14.2.1.3	Waterfall Plot of Percentage Change from Baseline in the Sum of Diameters – Rare Tumors – Response-Evaluable Analysis Set
14.2.2.1	Spider Plot of Percentage Change from Baseline in the Sum of Diameters Over Time – Response-Evaluable Analysis Set
14.2.2.1	Spider Plot of Percentage Change from Baseline in the Sum of Diameters Over Time – Gynaecological Indications – Response-Evaluable Analysis Set
14.2.2.1	Spider Plot of Percentage Change from Baseline in the Sum of Diameters Over Time – Rare Tumors – Response-Evaluable Analysis Set
14.2.3.1	Kaplan-Meier Plot of Duration of Response – Response-Evaluable Analysis Set
14.2.3.2	Kaplan-Meier Plot of Duration of Stable Disease – Response-Evaluable Analysis Set
14.2.3.3	Kaplan-Meier Plot of Duration of Response (iRECIST) – Response-Evaluable Analysis Set
14.2.3.4	Kaplan-Meier Plot of Progression Free Survival – Response-Evaluable Analysis Set
14.2.3.5	Kaplan-Meier Plot of Progression Free Survival (iRECIST) – Response-Evaluable Analysis Set
14.2.3.6	Kaplan-Meier Plot of Overall Survival – Response-Evaluable Analysis Set

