95% CI	XX.X, XX.X	XX.X, XX.X	XX.X, XX.X	XX.X, XX.X	XX.X, XX.X	XX.X, XX.X	XX.X, XX.X	XX.X, XX.X	XX.X, XX.X	XX.X, XX.X

Response as per RECIST v1.1: CR = Complete Response, PR = Partial Response, SD = Stable Disease, PD = Progressive Disease.

De-Diff LPS = Dedifferentiated Liposarcoma, UPS = Undifferentiated pleomorphic sarcoma, GCT = Germ Cell Tumors.

[1] 1 SD includes Stable Disease following one scan. 2 SD includes Stable Disease following 2 or more scans.

Note: Objective Response Rate is calculated as the number of subjects with a confirmed complete response or partial response divided by the number of subjects in the analysis set.

Note: Disease Control Rate is calculated as the number of subjects with a confirmed complete response, partial response or stable disease divided by the number of subjects in the analysis set.

Note: No subjects were recruited into Cohort D and so this cohort is not displayed.

Note: No subjects in Cohort B are in the Response-Evaluable Analysis Set and so this cohort is not displayed here.

Source: Listing 16.2.6.4.1

This table shell will be used for

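### ORR and DCR are tabulated only in the Response-Evaluable set, which drops some unscanned treated subjects; no all-treated result is planned, and two shell footnotes define the set differently

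*Protocol*

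**What the plan says.** Protocol Section 9.2, the synopsis in Appendix 9 and SAP Section 9 agree: "All efficacy analyses will be performed using the Response-Evaluable analysis set". Besides measurable disease at baseline and receipt of study drug, SAP Section 9 requires that a subject "had at least one post-baseline response assessment or discontinued treatment due to disease progression (including death due to disease progression) within 16 weeks" (plus a 2-week window) of the first dose.

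The outputs follow. In SAP Section 13.2 the response table is "Response – (RECIST v1.1) – Response Evaluable Analysis Set", and Tables 14.2.2.1 to 14.2.9 use the same set. So do the figures in Section 13.3, for example "Waterfall Plot of Percentage Change from Baseline in the Sum of Diameters – Response-Evaluable Analysis Set". The note to Table 14.2.1 divides confirmed complete or "partial response divided by the number of subjects in the analysis set". The ITT set serves only as the percentage denominator in the disposition table.

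Two provisions narrow the excluded group. Protocol Section 8.2 says "Response assessment and assessment of tumor markers will be obtained at treatment termination" (with exceptions where a recent scan or documented progression already exists). Section 6.1 says "Subjects who discontinue study treatment prior to confirmed progression of disease will continue to undergo radiographic and response assessments per protocol". A subject who gets either scan enters the set, and then Section 9.3.1 applies: "Subjects with not-evaluable response (NE) are counted as non-responders".

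For Cohort B (head and neck), SAP Section 10.1.2 drops columns for cohorts without subjects and names only Cohort D as having recruited nobody. Cohort B keeps its columns in the Safety-set shells. The note to Table 14.2.1 says that none of its subjects is in the Response-Evaluable set, so it is not shown there.

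**The concern.** The exclusion takes effect before the not-evaluable rule can. A subject who stops for toxicity, withdraws, is lost or dies of a cause other than progression, with no scan after baseline, is not counted as a non-responder but removed.

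That sits badly with two other parts of the protocol. Appendix 7 gives every included subject a response category and lists early death and missing assessments among the reasons for not evaluable. The interim rule in protocol Section 9.1 (and SAP Section 6.3) treats any discontinuation of study drug as sufficient data, so an unscanned toxicity dropout could count at stage 1 and be absent from the final ORR.

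SAP Section 10.1.3 plans no hypothesis test, so each cohort's ORR with its exact interval is the main result. At stake are an upward shift in that estimate, the lack of any summarised efficacy result for Cohort B, and a denominator described in two ways within one SAP.

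**Working it through.** **1. The plan's own figures.** For the Simon designs (10 subjects, then 29 in total), the probability of success is the sum over x ≥ r1 of Bin(10, x, p) × P[Bin(19, p) ≥ r − x].
- Type 1 (r1 = 1, r = 4): 0.0468 at p = 0.05 and 80.11% at p = 0.20.
- Type 2 (r1 = 2, r = 6): 0.0471 at p = 0.10 and 80.51% at p = 0.30.

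All four match protocol Section 9.1.

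**2. Direction.** Let N be the treated subjects, R the confirmed responders and m the unscanned subjects excluded. A confirmed response needs two assessments and stable disease needs at least one, so none of the m can be in a numerator. The all-treated rate is R/N and the reported rate is R/(N − m), a ratio of 1/(1 − d) with d = m/N. It is above 1 when m > 0; if R = 0, ORR stays at 0%. The same holds for DCR.

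The identity covers unscanned exclusions only. Someone excluded for lack of measurable disease at baseline (an eligibility deviation) may have been scanned and may have had disease control, so it does not apply there.

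**3. Size.** The documents give no observed d. Protocol Section 2.1 plans 115 evaluable subjects from 125 enrolled. As a rough proxy, d = 10/125 = 0.08 and 1/(1 − 0.08) = 1.087. It is rough because it is study-wide, starts from enrolled rather than treated subjects, and is not tied to the Response-Evaluable definition. For 29 subjects, 0.08 × 29 = 2.3, so two excluded is the nearest whole number. Three is shown for range. Intervals are 95% Clopper-Pearson.

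| Responders | All 29 treated | 2 excluded | 3 excluded |
|---|---|---|---|
| 4 | 13.8% (3.9–31.7) | 14.8% (4.2–33.7) | 15.4% (4.4–34.9) |
| 6 | 20.7% (8.0–39.7) | 22.2% (8.6–42.3) | 23.1% (9.0–43.6) |

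With two excluded the shifts are 14.8 − 13.8 = 1.0 and 22.2 − 20.7 = 1.5 points, against all-treated intervals 27.8 and 31.7 points wide. DCR moves more in points: an assumed 12/29 = 41.4% becomes 12/27 = 44.4%. In a cohort of 10 with one excluded, 1/10 = 10.0% (0.3–44.5) becomes 1/9 = 11.1% (0.3–48.2). With no responders only the upper limit moves, from 30.8% to 33.6%.

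These are illustrations. SAP Section 6.3 says the study was terminated and that only the cervical and uveal cohorts had a stage 1 evaluation.

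**4. The two definitions.**

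| | SAP Section 9 | Footnote [3], Table 14.1.1 and Listing 16.2.3 |
|---|---|---|
| Death | From progression | Cause not stated |
| Window | 16 weeks plus 2 | 16 weeks |
| Received study drug | Required | Not mentioned |

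Membership changes only for an unscanned death not due to progression within 16 weeks, or for a case in weeks 16 to 18. Separately, in Listing 16.2.3 footnotes [1] and [2] are swapped against the Safety and ITT column headings, which changes no result.

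**5. Can a reader rebuild the all-treated rate?** For whole cohorts, yes: responders from Table 14.2.1 over the Safety count in Table 14.1.1. For the Cohort F sub-cohorts, Table 14.1.1 has a single Cohort F column, so the denominators must come from Table 14.1.2.2. No exact interval on the all-treated denominator is tabulated anywhere.

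**The case against.** The set is pre-specified consistently in the protocol, its synopsis and the SAP. The objective is a preliminary assessment in single-arm cohorts. The definition already keeps subjects who stop for progression or die of it before a scan, and the termination and follow-up scans should leave few others outside. Counts that allow a rebuild are printed, and Cohort B's absence is openly footnoted. SAP Section 9 is the operative definition, and membership is checked at the Data Review Meeting and again on the locked database, so shell footnotes are unlikely to decide who is in. All of this stands and limits the weight of the point. It does not supply an all-treated rate with an interval, or remove the conflict with Appendix 7.

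Four stronger readings are tempting, and the documents do not support them.
- *The excluded subjects are known non-responders.* Their response was never assessed. They are non-responders by the protocol's not-evaluable convention.
- *The Simon type I error is inflated.* If all 29 counted subjects were response-evaluable and the null rate held among all treated, a 92% evaluable share would give 0.0601 and 0.0655. But protocol Section 9.1 builds both stages on enrolled subjects. Removing unscanned subjects does not change the responder count, and the SAP runs no test.
- *Two programmers would routinely get different primary rates.* Only the rare cases in step 4 differ.
- *Cohort B shows a lack of activity.* Its n is not given, and 0/n on few subjects says little: the exact upper limit is 97.5% for n = 1 and 70.8% for n = 3. The titles of the tumor listings carry no restriction to the set, so any recorded Cohort B assessments should still be listed.

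**Conclusion.** The point holds at minor to moderate severity. The primary estimate omits unscanned treated subjects whom the protocol's own convention would count as non-responders, so ORR and DCR can only be raised or left unchanged by those exclusions. At the planning proxy the rise is about 1 to 1.5 points of ORR at the design's success cut-offs in a cohort of 29, well inside the intervals. This assumes that 115 of 125 is a fair stand-in for the unknown excluded share and that the exclusions are unscanned rather than lacking measurable disease. The missing Cohort B summary and the footnote differences can be read directly from the SAP and need no assumption about the size of d. That Cohort B subjects were treated is inferred from its retained Safety-set columns.

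**What to change.** - Rerun the Table 14.2.1 shell on the Safety Analysis Set, by cohort and sub-cohort, with Clopper-Pearson intervals for ORR and DCR. Count a subject with no post-baseline assessment as not evaluable and hence a non-responder. Show it beside the Response-Evaluable result, which stays as planned.
- Include Cohort B. The expected entry is 0/n, to be confirmed from the data.
- Align footnote [3] of Table 14.1.1 and Listing 16.2.3 with SAP Section 9, and correct the swapped footnotes [1] and [2] in Listing 16.2.3.
- Record the added table in SAP Section 11. Protocol Section 9.3 allows analyses to be added in the SAP.

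The cost is one more table from an existing shell and some text edits, with no new data. The all-treated rates will be equal to or slightly lower than the Response-Evaluable ones, leaving aside any subject excluded for lack of measurable disease.

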9.3. Statistical Analyses

All statistical analyses for this study will be undertaken by a contract research organization under the supervision of sponsor personnel. Any data analysis carried out independently by the investigator should be submitted to the sponsor prior to publication or presentation.

All data will be listed. All trial endpoints will be described using summary statistics. Data will be summarized using descriptive statistics for continuous data (safety laboratory data, pharmacodynamic and relevant biomarker data), and contingency tables for categorical data

(demographics and other baseline characteristics, efficacy measurements, safety measurements and all relevant PK measurements.

For statistical analyses and summaries, baseline is defined as the available data from the last recorded measurement prior to first administration of study drug.

Details of statistical analysis and data reporting will be provided in a SAP document finalized prior to database lock. Additional analyses may be added in the SAP and tables, listings and figures shells will also be provided.

The SAP will be developed and finalized before database lock and will describe the selection of subjects to be included in the analyses, and procedures for accounting for missing, unused, and spurious data. Below is a summary of planned statistical analyses of the study endpoints.

9.3.1. Efficacy Analyses

Efficacy analyses will be performed separately for each cohort. RECIST 1.1 criteria will be used for the primary endpoint evaluation ([Eisenhauer et al., 2009](#)), and iRECIST will be used for the exploratory endpoint response evaluation ([Seymour et al., 2017](#)). The iRECIST endpoints are analyzed using the same statistical methodology and the results will be presented in the same ways for the corresponding RECIST 1.1 endpoints.

The primary efficacy endpoint is the ORR defined as the proportion of subjects who achieve confirmed CR or PR per RECIST v1.1. The best overall response is the best response recorded from the start of the treatment until PD. The smallest measurements recorded since the treatment started will be used as the reference for PD. Subjects with CR or PR are considered to have obtained objective response. Subjects with not-evaluable response (NE) are counted as non-responders. Exact 95% CI will be constructed for the ORR for each cohort.

Subjects with CR, PR or SD are considered to have achieved disease control. Disease control rate is defined as the proportion of subjects who have achieved CR, PR, and SD. Duration of response only applies to subjects whose best overall response is CR or PR and is defined as the number of days from the first documentation of objective tumor response to the date of first PD or death due to underlying cancer.

Duration of stable disease is measured from the start of the treatment (the first treatment date for non-randomized studies, the randomization date for randomized studies) until the date when the criteria for overall disease progression are first met.

Duration of response is the time from first evaluation showing CR or PR (response confirmation required at subsequent tumor assessment no earlier than 4 weeks after first evaluation showing CR or PR) to the time of the first subsequent evaluation showing PD or death. Only subjects who experience a confirmed CR or PR will be analyzed for DoR. Subjects who do not experience PD or death will be censored per the censoring rules in the statistical analysis plan.

Progression-free survival is defined as the number of days from Day 1 in Cycle 1 to the first documented progression or death due to any cause. Only deaths that occurred within 30 days of the last progression assessed.

Overall survival is defined as the time from the first dose of study drug to death due to any cause.

Overall survival, PFS, and DoR will be summarized for each group using Kaplan-Meier methodology. Censoring rules will be detailed in the statistical analysis plan.

- For analysis of OS, all subjects will be followed for survival for up to 2 years, until withdrawal of consent, loss to follow up, or death, whichever occurs first. At the time of analysis of OS, any subjects who remain alive will be censored at the last date they were known to be alive.
- PFS is the time from the start of study treatment to the first evaluation showing PD or death, whichever occurs first. Subjects who do not experience PD or death will be censored per the censoring rules in the statistical analysis plan.

